#### Inclusion and exclusion criteria:

Infants will be eligible for this study if they meet the following criteria:

- GA at birth: ≤32 weeks gestation and/or birthweight ≤1500 grams
- Infants 7 days or older
- Parental ability to perform the interventions or identified designated surrogate (e.g. grandparent)
- Abnormal writhing GMs defined by the presence of a poor repertoire pattern on 2 consecutive weeks or the presence of a cramped-synchronized pattern on any assessment (see **Figure 1**)

Infants will be excluded from the study if they are clinically unstable (requiring high frequency mechanical ventilation, vasopressor support, need for continuous intravenous pain or sedation medication), if their parents do not speak English or if parental participation is hindered (e.g. incarceration or work/personal related issues).

Figure 1: Intervention algorithm

Intervention (n=30): Parents will be provided oral as well as written (Flip book) and illustrated information about the interventions. Study team members will assist with demonstrating appropriate technique for applying interventions and will use the teach-back method to ensure comprehension and understanding. Interventions will be developmentally tailored to the infant's GA (Table 1) as follows:

1. Modified FNI portion of the bundle includes:

[figure not shown]
- a. Vocal soothing: mothers will be instructed to express their feelings to their infant in their native language using varying intonations
- b. Scent exchange: on initial visit, mothers will receive 2 cloths, 1 to place in her bra and 1 to place under her infant's head. Cloths are subsequently exchanged at each visit.
- c. Comforting touch: mothers will be instructed to use gentle but firm and sustained touch by placing the infant's arms on the chest and placing their hand on top. The other hand will be used to gently contain the infants' feet, lightly drawing the knees towards the chest.
- d. Mother-Kangaroo-Care plus: kangaroo care will be combined with gentle touch, vocal soothing and eye contact as described above.
- 2- Infant massage: mothers will be taught moderate pressure massage by PT
- 3- Parent-administered PT: 10 minutes interventions promoting postural and head control as well as midline orientation will be conducted by the mother is recommended starting at 33 weeks' PMA. The intervention will be monitored by a physical therapist for 3 consecutive sessions and weekly thereafter.

Mothers/Fathers whose infants are randomized to the intervention group will be encouraged to be at the bedside and provide the GA appropriate interventions once per day, 5 days per week (5/7).

Table 1: Developmental-Guided NICU based rehabilitation program

	Postmentrual Age (completed weeks)				
Interventions	23-25	26-28	29-32	33-36	≥37
Vocal soothing					
Scent exchange					
Comforting touch					
Kangaroo care plus					
Infant massage					
Parent-administered PT				_	

Standard of care (control group) (n=30): Parents of infants randomized to standard care will continue to be encouraged to touch, hold, and talk to their infants. They are also encouraged to perform kangaroo care based on unit guidelines. All infants in standard care will have a routine physical therapy consult at 28 weeks gestation. The infants will continue to be followed 2-3 times per week for 10-30 minutes per session by PT until discharge from hospitalization. Social work actively engages with parents of infants admitted to the NICU which will include the intervention and standard of care group. Social work provides ongoing parental support and strives to alleviate barriers to visitation. At time of discharge standard care will resume for both groups, which includes a referral to early intervention and a NICU follow up appointment with developmental pediatrics at 3 months PMA. Below is the study schedule.

Self-report activity logs (separately uploaded documents) will be used to monitor the fidelity of the program. Both groups will fill out the log and document what aspects of the program were performed, the date, and duration of the intervention. Weekly interviews will be conducted with parental participants to evaluate the acceptability (satisfaction), feasibility (practicality) and fidelity (engagement) of the program. Weekly interviews will be done at the bedside with parental participants and a research team member to discuss any challenges or barrier to applying the recommended evidence based practice interventions. Examples of interview questions are 1) How are things going? 2) Do you have any questions about the interventions? 3) Are there things that are preventing you from doing the interventions? Additionally, research team members will perform random direct observations of intervention application to further evaluate feasibility and fidelity.

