# Study goals and objectives

The goal of this project is to investigate the acceptability, feasibility and fidelity of an innovative NICU rehabilitation program that will include six multimodal, GA appropriate, parent-administered interventions (vocal soothing, scent exchange, comforting touch, kangaroo care, infant massage and physical therapy). We will also determine the effects of this program on short-term motor outcomes using the HINE, the GMA and the TIMP instruments in premature infants (≤32 week's gestation and/or ≤1500 grams birthweight).

AIM 1: Enroll 60 preterm infants (<32 weeks' gestation and/or ≤1500 grams) into a pilot RCT to evaluate the acceptability, feasibility (practicality) and fidelity (adherence, exposure and engagement) of a multimodal GA appropriate rehabilitation program during NICU hospitalization compared to standard of care. We will evaluate:

- Acceptability using recruitment, refusal, retention, and follow-up rates as well as weekly interviews with parental participants
- Feasibility (practicality) using direct observations and weekly interviews with parental participants
- Fidelity (adherence, exposure and engagement) using visitation data, activity logs, direct observations, and weekly interviews.

AIM 2: Examine the effect of a multimodal NICU-based rehabilitation program on short-term motor outcomes (general movements, cranial nerves, posture, movements, tone, and reflexes) of premature infants at risk for CP at discharge from the NICU and at 3 months PMA. We hypothesize that this type of GA appropriate multimodal NICU-based rehabilitation program will positively impact short-term motor outcomes by normalizing general movements and improving TIMP and HINE scores.

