# Safety considerations

Risk of loss of confidentiality and privacy

Risks related to the Maternal/Designee Activities with Baby:

Rare but serious:

- During Kangaroo Care there is a rare risk that infant may fall or that a tube or line may be dislodged.
- Injury to muscles or bones due to improperly applied infant massage

*General*:\_Infants in the NICU and family members are encouraged to participate in developmentally appropriate activities. However, these activities are not applied in a systematic fashion. The intervention group is at no greater risk than the standard care group as interventions evidence based and has been applied in the NICU setting.

Adverse events are monitored for the entirety of the study.

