#### Data management and statistical analysis

IRB approval and informed consent will be obtained prior to the start of the study. Video recorded GMA is standard of care in the NICU for neonates born ≤32 week's gestation and/or ≤1500 grams birthweight. Videos will be reviewed and scored independently by at least 2 of the study investigators. Videos will be scored with only the PMA information available to the investigator at the time of review. Inter-rater and intra-rater agreement will be assessed using Cohen's kappa (kappa) and percentage agreement. In case of

disagreement, the videos will be reviewed by all study members trained in the GMA and a consensus will be obtained.

The UVA NICU admits an average of 112 very low birth weight infants every year among which 83 are born at 32 weeks' gestation or less. We anticipate that, in one year of accrual, there will be approximately 120 infants <32 weeks gestation and/or ≤1500g birth weight. Based on a preliminary assessment of children in the NICU, we expect that 80% of these children will be eligible for the study. Recruitment acceptance rates of previous studies conducted in our NICU range from 30-50% for intervention studies and 80-90% for noninvasive studies. Using an acceptance rate of 80% yields an expected accrual of 70 patients per year. Allowing for 10% dropout, accrual of 33 patients per group (power calculation below) can be completed in 1 year.

Quantitative data will be analyzed using descriptive statistics and content analysis will be performed for qualitative responses. Quantitative data will be analyzed using the newest version of SPSS. Due to the exploratory purpose of the specific aim, descriptive statistics will be computed for all quantitative variables (demographic characteristics, recruitment, refusal, retention, follow up rates, % completion of self-report log and number of visitations per unit log). Frequencies and rates will be calculated for categorical variables and means and standard deviations will be calculated for continuous variables.

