### Expected outcomes of the study

Acceptability, feasibility and fidelity will be evaluated to ensure that the study design is sound for a future full-scale intervention study, Table 2.

- Acceptability using recruitment, refusal, retention, and follow up rates as well as weekly interviews with parental participants
- Feasibility (practicality) using direct observations and weekly interviews with parental participants
- Fidelity (adherence, exposure and engagement) using visitation data, activity logs, direct observations, and weekly interviews

Table 2: Primary outcomes

Variable	Concept	Domain	Metrics
Acceptability	Satisfaction	Correct, consistent and continuous use of the program	1. ≥75% Recruitment rates 2. <10 % Refusal rates 3. 75% Retention rates
			

4. 90% Follow-up rates

5. Weekly interviews with parental participants

Feasibility	Practicality	Adequacy of the logistics a) determining the capability of carrying out the program as planned b) identifying difficulties in applying any aspect of the program	Direct observations     Weekly interview the parental participants
Fidelity	Adherence	a) pro portion of the program content, b)methods and c) activities	1.>75% Completion of self-report activity log to be completed by parental participant 3.Direct observations by research team member
Fidelity	Exposure	a) number of sessions, b) attendance, c)frequency and d) duration	1. Self-report activity log to be completed by parental participant 3. Direct observations by research team member 4. Administrative data (NICU visitation log)
Fidelity	Engagement	Participation in the program	1. Weekly interviews conducted by research team member with parental participants 2. Administrative data (NICU visitation log) 3. >75% Completeness of the activity logs

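### The >75% adherence criterion tests whether the log was filled in, not what was delivered, so it cannot show that the arms differed

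*Combined protocol and SAP*

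**What the plan says.** - **Program.** Study goals and objectives lists six parent-administered components: "vocal soothing, scent exchange, comforting touch, kangaroo care, infant massage and physical therapy". Intervention parents are asked to deliver those suited to the infant's age once daily on five days out of seven. Parent-administered physical therapy (PT) starts at 33 weeks' postmenstrual age (PMA).
- **Control arm.** The standard-of-care paragraph states: "Parents of infants randomized to standard care will continue to be encouraged to touch, hold, and talk to their infants". It adds: "They are also encouraged to perform kangaroo care based on unit guidelines". Therapist-delivered PT is also part of usual care: "The infants will continue to be followed 2-3 times per week for 10-30 minutes per session by PT until discharge".
- **Regularity of usual care.** Safety considerations says that NICU families in general are encouraged in such activities, and then: "However, these activities are not applied in a systematic fashion".
- **What is recorded.** Both groups fill in the activity log and "document what aspects of the program were performed, the date, and duration of the intervention".
- **What is tested.** Table 2 describes the adherence domain as the share of the program's content, methods and activities. Its only numeric criterion there is ">75% Completion of self-report activity log to be completed by parental participant". The engagement row repeats a 75% criterion for completeness of the logs. The exposure row draws on the log but has no threshold.
- **What is analyzed.** In Data management and statistical analysis, the log enters the list of descriptive variables only as the percentage "completion of self-report log and number of visitations per unit log".

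**The concern.** The domain and the metric in the adherence row do not match. The domain is about delivery of the program; the metric is about completion of a form. Table 2 is meant to show whether the design is sound for a full-scale trial, so a pass on this row will be read as evidence that the program was delivered.

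The overlap with usual care sharpens the problem. If control parents already talk to, touch, hold and give kangaroo care to their infants, the contrast between arms rests on two things. One is the three components absent from the usual-care description (scent exchange, massage, parent-administered PT). The other is how specifically and regularly the shared three are done. The planned log statistic shows neither.

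**Working it through.** **1. The plan's own figure.** The 75% threshold is set without derivation, and no numerator or denominator is given, so there is nothing to reproduce. Below, completion is taken in its ordinary sense: log days filled in divided by log days expected. That is an assumption.

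**2. Overlap by component.**

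| Component | Counterpart in usual care? | What the program adds |
|---|---|---|
| Vocal soothing | Yes, talking | Instructed, with varied intonation |
| Comforting touch | Yes, touching and holding | A specific two-handed containment |
| Kangaroo care | Yes, per unit guidelines | Combined with touch, voice and eye contact |
| Scent exchange | Not described | Whole component |
| Infant massage | Not described | Whole component |
| Parent-administered PT | Therapist PT only | Delivery by the parent |

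The overlap is 3/6 = 50% by name. It is an overlap in kind, not identity.

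**3. What completion can and cannot show.** Take one week after 33 weeks' PMA with five program days, and assume all six components are due.

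| Case | Log completion | Voice, touch, kangaroo care | Scent, massage, parent PT |
|---|---|---|---|
| A. Intervention parent does only the shared three, logs every day | 5/5 = 100%, pass | 5/5 each | 0/5 each |
| B. Intervention parent does all six, logs every day | 5/5 = 100%, pass | 5/5 each | 5/5 each |
| C. Control parent does the usual-care forms, logs every day | 5/5 = 100%, pass | 5/5 each | 0/5 each |
| D. Intervention parent does all six, logs three days | 3/5 = 60%, fail | 5/5 each | 5/5 each |

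A, B and C are indistinguishable on completion, although B delivered the program and A did not. C shows that the two arms can have the same figure. D shows the error in the other direction: full delivery fails because the form was not filled in. Counting fields instead of days does not rescue A, because a field answered as not done is still completed.

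**4. Do the other sources close the gap?** Direct observations are random, with no stated number, component criterion or threshold. Visitation data count presence, not content. Interviews are qualitative. Therapist monitoring of parent-administered PT (three sessions in a row, then weekly) covers one component and is not tied to a fidelity statistic. No section plans a summary by component, a threshold by component, or a comparison of logged components between arms.

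**The case against.** The strongest reply is that fidelity is wider than one log figure. Table 2 also has exposure (sessions, attendance, how often, how long), direct observation, visitation data and interviews, and the log records individual activities in both arms. That stands: the data are collected, and the gap lies in the planned summary and criterion. It does not remove the point, because none of these sources carries a delivery criterion, and the one number that decides adherence can be met without delivery.

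A second reply is that the shared components are not really shared. The program versions are taught, specific and scheduled, while usual activities are not systematic. That also stands, and the overlap should be described as one in kind. But if specificity and regularity are the contrast, delivery by component and arm is what would help show it.

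A reader might go further and take the 75% as delivery averaged over the six components, so that usual-care activities carry the figure while the new ones are largely undelivered. The documents do not support this. No such average is defined, and the arithmetic does not bear it out. With equal weights (an assumption) and the shared three at 100%, the new three at 0% give 3/6 = 50%, and at 25% give (3 + 0.75)/6 = 62.5%. Both fail, and passing needs more than 50%. With five components due the figure is (0.75 × 5 − 3)/2 = 37.5%. With four due, zero delivery of the one new component gives 3/4 = 75%, which does not exceed 75%. The last two cases also depend on Table 1 shading that is not readable here.

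**Conclusion.** The point holds in this form. The adherence criterion, and the only log statistic in the analysis section, measure completion of a form. A result of 100% is compatible with anything from 0% to 100% delivery of any component, and with equal figures in both arms. Three of the six components overlap in kind with usual care, so log completion cannot show that the arms differed in what was delivered.

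This rests on completion having its ordinary meaning. The log form is a separate document that was not available; if it defines completion as delivery, the plan needs to say so. The conclusion does not depend on the ages at which Table 1 opens each component.

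Two stronger conclusions should not be drawn. A reader might infer that a null motor result could never be separated from non-delivery. The logged activities would allow that question to be examined; the plan just does not commit to it. A reader might also infer that control infants receive half the program, but the more specific program versions and the unsystematic nature of usual care contradict that. Motor outcomes are secondary, and the HINE power calculation is unaffected.

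**What to change.** In Data management and statistical analysis and in Table 2:

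1. Keep log completion as a data-quality measure, with a stated numerator and denominator.
2. Define adherence and exposure from the existing log as days each component was delivered divided by days it was due, taking due days from Table 1 at the infant's PMA and the plan's own five-of-seven-day schedule. State how days without a log entry are counted.
3. Report this for each of the six components by arm. That schedule is set for the intervention arm only, so in the control arm the same denominator serves as a common yardstick, not as an adherence test.
4. Judge the >75% adherence criterion on delivery in the intervention arm, shown component by component, with direct observations as a check. Keep all six components in the test; limiting it to the three without a usual-care counterpart would leave half of the defined program unexamined.

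The cost is plan wording, a longer fidelity table and possibly a lower headline adherence figure. No new data collection is needed if the log form records what the protocol says it does, and treatment is unchanged.

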# Safety considerations

Risk of loss of confidentiality and privacy

Risks related to the Maternal/Designee Activities with Baby:

Rare but serious:

- During Kangaroo Care there is a rare risk that infant may fall or that a tube or line may be dislodged.
- Injury to muscles or bones due to improperly applied infant massage

*General*:\_Infants in the NICU and family members are encouraged to participate in developmentally appropriate activities. However, these activities are not applied in a systematic fashion. The intervention group is at no greater risk than the standard care group as interventions evidence based and has been applied in the NICU setting.

Adverse events are monitored for the entirety of the study.

# Follow up

Interventions will be completed upon discharge from the NICU. Usual care resumes for both groups at discharge. Outpatient follow up for secondary developmental outcomes will occur at 3-4 month follow up appointment (see study schedule).

#### Data management and statistical analysis

IRB approval and informed consent will be obtained prior to the start of the study. Video recorded GMA is standard of care in the NICU for neonates born ≤32 week's gestation and/or ≤1500 grams birthweight. Videos will be reviewed and scored independently by at least 2 of the study investigators. Videos will be scored with only the PMA information available to the investigator at the time of review. Inter-rater and intra-rater agreement will be assessed using Cohen's kappa (kappa) and percentage agreement. In case of

disagreement, the videos will be reviewed by all study members trained in the GMA and a consensus will be obtained.

The UVA NICU admits an average of 112 very low birth weight infants every year among which 83 are born at 32 weeks' gestation or less. We anticipate that, in one year of accrual, there will be approximately 120 infants <32 weeks gestation and/or ≤1500g birth weight. Based on a preliminary assessment of children in the NICU, we expect that 80% of these children will be eligible for the study. Recruitment acceptance rates of previous studies conducted in our NICU range from 30-50% for intervention studies and 80-90% for noninvasive studies. Using an acceptance rate of 80% yields an expected accrual of 70 patients per year. Allowing for 10% dropout, accrual of 33 patients per group (power calculation below) can be completed in 1 year.

Quantitative data will be analyzed using descriptive statistics and content analysis will be performed for qualitative responses. Quantitative data will be analyzed using the newest version of SPSS. Due to the exploratory purpose of the specific aim, descriptive statistics will be computed for all quantitative variables (demographic characteristics, recruitment, refusal, retention, follow up rates, % completion of self-report log and number of visitations per unit log). Frequencies and rates will be calculated for categorical variables and means and standard deviations will be calculated for continuous variables.

Qualitative analysis will included semi-structured interviews with adult participants as well as direct observations using qualitative description. Qualitative descriptive analysis will provide a comprehensive evaluation of the NICU multimodal rehabilitation program. The textual data from the interviews and observation notes will be analyzed by (1) immersion in the data (2) followed by line by line analysis and data reduction of the textual data through inductive open coding and constant comparative analysis. Tentative categories will be listed with each line of data and identified by "nodes" in the Dedoose software. (3) After line-by-line analysis of the transcripts, categories ("nodes") will be grouped together to form tentative themes.

Repeated measures models will be used to compare HINE and TIMP total scores at the time of discharge and at 3 months PMA between newborns in the standard care group and in the intervention group (NEO rehab program). F-tests based on contrasts will be used to make comparisons at the two specific time points. To approximate the power of the F-test for comparing the groups with respect to the 3-month HINE scores, the results in Romeo et al.(2008) were used. Their study showed that across CP diagnoses, the average 3 –month HINE score was approximately 40 with an estimated standard deviation of 8.8. A score of below 40 is associated with the GMFCS IV and V levels while a score of 40-60 is associated GMFCS levels I and II at 3 months of age. A score ≥ 73 is optimal. With 30 subjects per group, the two-sample t-test has 80% power, with a 2-sided significance level of 5% when the effect of the intervention is to increase HINE scores by 6.5 points. Allowing for 10% dropout, 33 patients per group are required. Similar analyses will be used for the TIMP scores as well as subscales of the HINE. For the GMA assessments, we will tabulate the proportion of children in each group classified as having poor repertoire, cramped/synchronized or chaotic movement abnormalities at each of the followup times. Markov models will be used to assess how the intervention affects the proportions of children transitioning between classifications. For all of the endpoints; this study will provide estimates of variation useful for planning a larger study of the rehabilitation program. Our primary analysis will be done as intention-to-treat.

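### The visit count and the number of sessions have no denominator for time in hospital after randomisation, so they mix length of stay with engagement

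*Combined protocol and SAP*

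**What the plan says.** The section on data management and statistical analysis names the quantitative variables to be described. The two that concern fidelity are "completion of self-report log and number of visitations per unit log", the first being a percentage. For the summary statistic it says "means and standard deviations will be calculated for continuous variables".

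Table 2 (Expected outcomes of the study) gives the exposure domain as "a) number of sessions, b) attendance, c)frequency and d) duration" and lists the NICU visitation log as a source for both exposure and engagement. Engagement also rests on weekly interviews and on ">75% Completeness of the activity logs". All of these sit under the primary outcomes.

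The period over which visits and sessions can accrue has no fixed length. The eligibility criteria ask for "Infants 7 days or older", with no upper age, and for abnormal writhing movements: poor repertoire in two consecutive weeks, or a cramped-synchronized pattern at any assessment. At the other end, the Follow up section says "Interventions will be completed upon discharge from the NICU". NICU length of stay is collected with the demographic data, but nothing links it to visits or sessions.

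**The concern.** A count accrued over an unequal window is the product of a rate and a duration. Here the rate is what the pilot wants to learn (how often families come and deliver the program), and the duration depends mainly on how immature the infant was and when it qualified. A mean number of visits with its SD does not separate the two.

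Two uses of the number suffer. First, exposure and engagement are primary-outcome domains, and a reader cannot tell from a mean visit count whether families came often or infants stayed long. Second, the analysis section promises, for all endpoints, estimates of variability for designing a larger study. The SD of a raw count would carry the spread in stay into that design.

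**Working it through.** The plan gives no figure for time from randomisation to discharge or for expected visits, so there is no figure of its own to reproduce on this point. What follows is a set of ranges under stated assumptions.

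**1. Length of the window.** Window in weeks = discharge PMA − (gestational age at birth + lag to entry). Planned sessions = 5 × window, from the protocol's once daily on 5 of 7 days.

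Inputs:
- Births at 23, 28 and 32 weeks are assumed. 23 is the lowest age in Table 1, and 32 is the gestational-age limit.
- A lag of 1 to 2 weeks is assumed. One week is the minimum under the age criterion.
- Discharge at 36 to 38 weeks is assumed. The Innovation section gives 35 to 38 weeks, but for a cited nurture programme, not for this trial.

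| Births compared (weeks) | Discharge (weeks) | Lag (weeks) | Windows (weeks) | Ratio | Planned sessions |
|---|---|---|---|---|---|
| 28 v 32 | both 38 | 1 | 38−29 = 9 v 38−33 = 5 | 1.8 | 45 v 25 |
| 28 v 32 | both 36 | 2 | 36−30 = 6 v 36−34 = 2 | 3.0 | 30 v 10 |
| 23 v 32 | both 38 | 1 | 38−24 = 14 v 38−33 = 5 | 2.8 | 70 v 25 |
| 23 v 32 | both 36 | 2 | 36−25 = 11 v 36−34 = 2 | 5.5 | 55 v 10 |
| 23 v 32 | 38 v 35 | 1 | 38−24 = 14 v 35−33 = 2 | 7.0 | 70 v 10 |

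Every infant in this table has full adherence, so the rate is 5 per week, or 100% of plan, throughout. Later entry widens the extremes (the last row at a 2-week lag is 13 v 1 weeks), but a ratio over a one-week window is fragile and I do not rely on it.

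**2. How much of the count is stay.** Let count = R × W, with visiting rate R independent of window W. Then Var = μ_R²σ_W² + μ_W²σ_R² + σ_R²σ_W², and the share explained by weeks is μ_R²σ_W² / Var.

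Assume a mean of 4 visits per week with SD 1, and W uniform on 2 to 12 weeks (mean 7, variance 100/12 = 8.33):
- Var = 16 × 8.33 + 49 × 1 + 8.33 × 1 = 133.3 + 49 + 8.3 = 190.7
- Share from weeks = 133.3/190.7 = 70%
- Share from rate = 49/190.7 = 26%

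A simulation with rates truncated to 0–7 per week gives these shares (weeks / rate):

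| Window (weeks) | Rate SD 0.5 | Rate SD 1 | Rate SD 1.5 |
|---|---|---|---|
| 2–12 | 90% / 8% | 70% / 25% | 52% / 41% |
| 3–9 | 83% / 16% | 55% / 41% | 36% / 59% |
| 4–8 | 70% / 30% | 37% / 61% | 21% / 76% |

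Stay often dominates. It does not when windows are narrow or visiting habits vary widely.

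**3. The planning SD.** With windows of 2–12 weeks and rate SD 1, the coefficient of variation is 0.49 for the count and 0.25 for the rate. About half the relative spread a planner would read off the count is absent from the rate.

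**4. The arm comparison.** With the same windows (SD √8.33 = 2.89 weeks) and 30 per arm, the standard error of the difference in mean stay is 2.89 × √(2/30) = 0.75 weeks. The 95% chance range is about ±1.5 weeks. At 4 visits per week that is about ±6 visits on a mean of 4 × 7 = 28, or about 21%, with identical engagement in both arms. It is centred on zero, and stratification by birth weight would narrow it.

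**The case against.** The strongest reply is that the plan is not confined to raw counts. Table 2 names attendance, frequency and duration, log completion is a percentage, and the activity logs record date and duration. Engagement is also judged by interviews and log completeness. The visit count has no target, the plan does not rank families, and no between-arm test uses the count. These variables are declared exploratory and descriptive, and length of stay is collected and could be printed alongside.

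Much of this stands, and it rules out several stronger readings that a reader might infer:
- *That the count measures stay instead of engagement.* It carries both, in proportions that depend on assumptions (21% to 90% from stay above).
- *That all of exposure is a bare count.* Only the visit number is specified that way in the analysis section; number of sessions is one item of four in Table 2.
- *That the several-fold spread is a documented fact.* It is inferred, and the only discharge age in the documents belongs to another programme.
- *That families would be misranked.* Full adherence over 2 weeks gives 10 sessions and half adherence over 8 weeks gives 20, but the example is invented and no planned analysis ranks anyone.
- *That the arm comparison is biased.* That would need the program to change length of stay, which the documents do not hypothesise.

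The reply does not remove the problem. Frequency and log completion are named without a denominator, and frequency is not in the analysis section's variable list. Interviews and log completeness do not correct the visit count. Length of stay printed as a separate mean does not recover each infant's rate.

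**Conclusion.** The point holds in a limited form. As written, the plan summarises visiting by mean and SD with no allowance for a window that opens at a variable time and closes at discharge. Number of sessions has the same gap. The window differs roughly 2- to 7-fold between infants, on assumed births at 23 to 32 weeks and discharge at 35 to 38 weeks; the actual distribution is unknown from the documents. The count and its SD therefore mix stay with engagement. The consequence is a primary-outcome descriptor that is hard to interpret, a planning SD that may be inflated, and a noisier arm comparison. It is not a systematic bias between arms. The change is worth making because a better measure is available at almost no cost.

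**What to change.** State in the analysis section that, for each infant, the window is the number of in-hospital days from randomisation to discharge, transfer or death. Then:

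- In both arms, report visits (or visit-days) divided by days in the window.
- In the program arm, report sessions delivered divided by sessions planned, where planned = days in the window × 5/7, using the protocol's own schedule.
- Use the same window as the denominator for log completion.
- Summarise these by arm next to the raw counts and the window length. Rates from very short windows are unstable, which is a further reason to show window length.

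Agreement between the self-report logs and the unit visit log may be reported as a descriptive cross-check. It should not be used to exclude sessions: the documents do not show that the unit log is complete, dated by day or inclusive of surrogate visits, so such a rule could delete real sessions.

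The cost is a small amount of extra analysis. The listed item is NICU length of stay, so the window has to be derived from the randomisation date and the date of discharge, transfer or death.
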